8.3.3 Covariate Assessment

Covariates are needed to understand the generalizability of study results. Covariates will be assessed during the baseline period. For covariates that can change over time the value at index date will be used; however, if unavailable at index date then the date most proximal to (preceding) index date will be used.

- Demographic and clinical characteristics
 - Age in years at index date
 - Sex (male, female, unknown)
 - Smoking status (current smoker, former smoker, never smoker, unknown/not documented) at index date
 - BMI in kg/m² at index date
 - ECOG performance score (0, 1, 2, 3, 4, missing/unknown) at index date
 - PD-L1 tested (yes, no)
 - PD-L1 expression, among tested (percent of positive tumor cells for the sample by PD-L1 staining/testing: < 1%, 1 - < 50%, ≥ 50%, or no valid test result)
 - Lab test (ie, blood routine test, urine routine test, blood biochemistry, etc.), ECG, and radiology at baseline

Protocol Number: 20240175

Date: 27 March 2025 Page 24 of 47

Prescence of brain metastases (if information is available)

- Prior lines of therapy
- Concomitant medications and comorbidities
- Diagnosis and tumor-related characteristics
 - Time since advanced NSCLC diagnosis
 - Stage at sotorasib initiation (American Joint Committee on Cancer staging; Stage 0, 1, 2, 3, 4, unknown) (further granularity of staging data may be available)
 - Histology (non-squamous cell carcinoma including adenocarcinoma, large-cell carcinoma, others; squamous cell carcinoma; not otherwise specified)
- Tumor specimen-related characteristics
 - Presence of actionable gene alterations: mutations or re-arrangements (eg, ALK, EGFR, ROS proto-oncogene 1, BRAF)
- Treatment-related characteristics
 - Type of regimen sotorasib is used as (eg, monotherapy, combination therapy)
 - Treatment patterns: Available treatment history from site records will be extracted on all patients. Prior treatment history will include systemic anticancer treatments which are generally grouped as chemotherapies, targeted therapies, immunotherapies and others with examples listed below:
 - Chemotherapy
 - Platinum-based chemotherapy
 - Targeted therapy (eg, anti-EGFR, etc.)
 - Immunotherapy
 - PD-1/PD-L1 checkpoint inhibitors
 - Others

8.3.4 Validity and Reliability

In BOAO Pilot Zone, both structured and unstructured data elements will be extracted and validated. Any suspected data abstraction errors will be checked, confirmed or corrected with the clinical investigators responsible for the study operation, by checking the original copy. Unstructured data, which include details not directly captured in a

Protocol Number: 20240175

Date: 27 March 2025 Page 25 of 47

structured electronic health record field, such as description of AEs in the medical records will require some level of manual abstraction. All abstractors will undergo systematic training before performing data extraction. Besides, key information such as grade of AEs will be verified by investigators.

In Hong Kong SAR, the CDARS database has been used to conduct high quality real-world studies (Chan et al, 2015; Chan et al, 2016; Lau et al, 2017; Man et al, 2017; Wong et al, 2016). Data validation has demonstrated high coding accuracy in CDARS (Chan et al, 2015; Chan et al, 2016; Wong et al, 2016).

8.4 Data Sources

In BOAO Pilot Zone, patients, often residing from across mainland China, need to be physically admitted to one of the several hospitals in BOAO Pilot Zone to receive sotorasib. The first hospitalization includes a complete medical history, radiology scans, tumor biomarker assessment, and liver and renal function tests to inform clinicians' decision to treat. As sotorasib is in the pre-registration program, the government requires close monitoring and reporting of safety events, which are well documented in the established hospital system. Hence, expectation that safety endpoints will be measured adequately in this study. As sotorasib is an oral medication taken daily until disease progression or unacceptable toxicity, patients need to physically return to the BOAO Pilot Zone hospital at least once per month initially, and every 3 months thereafter based on physician's assessment and justification, to continue therapy. Patients seeking refills require recent radiology results, organ function evaluation etc. reassessment. Refills can be initiated with online evaluations and subsequently processed through outpatient clinics at hospitals in Hainan. Reports from Tier A hospitals across China are accepted. A case report form created for this study will be used to extract the relevant structured and unstructured data from the electronic heath record.

In Hong Kong SAR, this study will be using the electronic health records of the CDARS database managed by the Hong Kong Hospital Authority, a statutory body in charge of all public hospitals and their ambulatory clinics in Hong Kong SAR. Anonymized patient data are transferred daily to CDARS for audit purposes from the clinical management system (CMS) of the Hospital Authority, which contains medical records including: demographic information, diagnoses, prescription records, laboratory tests, accident and emergency attendance, outpatient clinics, hospital stay, and discharge information of patients since 1993. It also contains data on causes of death through its internal linkage

Protocol Number: 20240175

Date: 27 March 2025 Page 26 of 47

to regional deaths registry from the Immigration Department. Hence, expectation that OS will be measured with complete follow-up. A unique reference number is assigned to each patient for identification and data retrieval purposes. The structure data within CDARS will provide most of the relevant data for study, the unstructured clinical notes within the electronic health record (Electronic Patient Record/Clinical Management System [EPR/CMS]) will also be used to augment information on key covariates. Electronic patient record (EPR) consolidates individual patient health records from various sources, including hospitals, clinics, and primary care providers, into a single electronic record, providing a comprehensive view of a patient's medical history.

8.5 Study Sample Size

This is a descriptive study in which patient-level data on safety, OS, CCI

By the time of data cut-off, there will be approximately 100 sotorasib treated patients in BOAO Pilot Zone assuming all sites are eligible, and about 15 patients in Hong Kong SAR, will be eligible for enrollment.

The estimation precision of parameters is provided based on the preliminary sample count of all patients treated with sotorasib in BOAO Pilot Zone and Hong Kong SAR. The formular, based on the normal approximation to the binomial distribution, for calculating the precision (ie, margin of error, which is represented by one half the desired width of the confidence interval) given a proportion and sample size is as the following:

$$e = \sqrt{\frac{px (1-p)x (Z_{1-\frac{\alpha}{2}})^{2}}{n}}$$

Where P is the expected proportion of interest, n is the sample size, and $Z_{1-\frac{\alpha}{2}}$ is the standard normal Z value corresponding to a cumulative probability of $(1-\frac{\alpha}{2})$ (eg, if α = 0.05 then Z=1.96). The following table (Table 1) provides the estimated precision based on the sample size of patients who received sotorasib (N = 115, tentatively) and various proportions of interest.

Protocol Number: 20240175

Date: 27 March 2025 Page 27 of 47

Table 1. Precision based on the sample size by various proportions

Proportion (1- proportion)	Sample size of patients	The margin of error (absolute precision)
50% (50%)	115	9.14%
40% (60%)	115	8.95%
30% (70%)	115	8.38%
20% (80%)	115	7.31%
10% (90%)	115	5.48%

As the proportion of interest (p) (eg, proportion of treatment-related AEs of grade 3 or worse) in this study is not known in advance, we consider the proportion to be 50% (maximum uncertainty). Such an assumption yields the most conservative, ie, the largest level of margin of error (indicating the lowest level of precision), with is $\pm 9.14\%$.

The sample size of patients treated with sotorasib will be confirmed during data cleaning and data analysis phase.

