- Last treatment with sotorasib + 30 days

As the Hong Kong SAR CDARS database is a closed-loop database with linkage to the regional deaths registry, patients without evidence of death in the CDARS database by the data cut-off date were considered alive, and their last activity date will be the same as the cut-off date.

For objective of OS, follow-up per patient will continue through earliest date of last clinical activity in the data source, data cut-off in the data source, or death.

Variables

Outcomes:

- Primary: The patient incidence of AEs after sotorasib initiation.
- Secondary: OS from clinician notes in electronic health record and linkage to mortality records (where available).
- Exploratory: CCI

 CCI

Exposure:

o Use of sotorasib

Protocol Number: 20240175

Date: 27 March 2025 **Page 14 of 47**

Covariates

Key demographic, clinical characteristics, and pathology covariates including and not limited to age, sex, smoking status, body mass index (BMI), Eastern Cooperative Oncology Group (ECOG) performance status, histology, tumor stage, programmed death-ligand 1 (PD-L1) protein expression, presence of tumor mutations or rearrangements, laboratory test, electrocardiogram (ECG) and radiology, prior systemic treatments, brain metastases (if information available), prior lines of systemic therapy, and concomitant medications.

Study Sample Size

By the time of data cut-off, an estimated about 100 and 15 patients will have been treated with sotorasib and eligible for study inclusion from BOAO Pilot Zone and Hong Kong SAR, respectively. For a sample size of 115 patients and the observation of a proportion of 50% patients with an endpoint the largest level of margin of error (indicating the lowest level of precision) is \pm 9.14%.

Data Analysis

Frequencies will be presented for categorical demographic, clinical, and pathological variables. Descriptive statistics (mean, median, standard deviation, and range) will be presented for continuous variables.

The patient incidence of AEs will be summarized by count and proportions, specifically the proportion of patients experiencing AEs relative to the total number of patients. Median OS and PFS, along with the corresponding 95% confidence intervals (CIs) will be calculated using Kaplan-Meier estimates. The estimated survival probabilities, along with the corresponding 95% CIs will be presented for patients at 6 and 12 months.

CC

5. Amendments and Updates

None

6. Rationale and Background

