8.3.2 Outcome Assessment

Safety Outcomes

In BOAO Pilot Zone, the AEs recorded in the electronic health record database throughout the study period will be documented and analyzed. Detailed information in medical records including vital signs, concomitant treatments, results of routine laboratory testing, ECG, and radiology will be reviewed to verify these AEs. Severity grade of AEs will be further verified by investigators according to the Common Terminology Criteria for Adverse Events (CTCAE), version 5.0 (CTCAE v5.0).

The patient incidence of AE after sotorasib initiation, including:

- TEAE
- Adverse event of interest, inclusive of hepatotoxicity, interstitial lung disease/pneumonitis, and renal toxicity
- Treatment-related AEs
- Treatment-related AEs of grade 3 or worse
- Serious treatment-related AEs
- Treatment-related AEs leading to treatment discontinuation
- Treatment-related AEs leading to dose reduction
- Treatment-related AEs leading to death

[figure not shown]
In Hong Kong SAR CDARS database, only adverse event of interest, inclusive of hepatotoxicity, interstitial lung disease/pneumonitis, and renal toxicity will be documented and analyzed. Each event of interest is a grouping of individual preferred terms determined using the following standardized MedDRA queries (SMQs): drug-related hepatic disorders – comprehensive search (SMQ narrow) for hepatotoxicity; interstitial lung disease (SMQ narrow) for ILD/pneumonitis; and acute renal failure (SMQ narrow) for renal toxicity. Medical records including diagnosis, vital signs, concomitant treatments, results of routine laboratory testing, ECG, and radiology will be reviewed to identify and verify AE. Detailed testing and exams to review will be further clarified in the statistical analysis plan and eCRF.

Protocol Number: 20240175

Date: 27 March 2025 Page 23 of 47

OS

• OS: The time from the index date to death from any cause. Patients without evidence of death at data cutoff will be right-censored at their last activity date.

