8.7.2 Planned Method of Analysis

8.7.2.1 General Considerations

All data analyses will be performed using appropriate software such as SAS statistics software version 9.3 or higher (SAS Institute Inc., Cary, NC). An analysis plan with a detailed description of analyses to be performed will be developed.

All analysis will be conducted separately for patients in BOAO Pilot Zone and Hong Kong SAR CDARS.

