8.7.3 Analysis of Safety Endpoints

All patients participating in the study who meet the eligibility criteria will be included in the safety analysis. All AEs will be coded using MedDRA. For safety outcomes defined in Section 8.3.2, count and proportions will be calculated, respectively.

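### The only stated precision (±9.14% at N = 115) is for a pooled cohort that no planned analysis uses: the regions are analysed separately, and the example endpoint is collected in BOAO only

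*Protocol*

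**What the plan says.** Protocol section 8.5 sets out the expected number of patients as follows: "there will be approximately 100 sotorasib treated patients in BOAO Pilot Zone assuming all sites are eligible, and about 15 patients in Hong Kong SAR". It adds the two counts and gives the "estimated precision based on the sample size of patients who received sotorasib (N = 115, tentatively"). Table 1 runs from a proportion of 50% (±9.14%) to 10% (±5.48%), all at 115 patients. The text names the proportion with grade 3 or worse treatment-related events as its example and presents ±9.14% as the largest margin. The abstract carries the same headline: "For a sample size of 115 patients and the observation of a proportion of 50% patients with an endpoint".

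Three other places determine which patients enter which analysis:

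- Section 8.7.2.1: "All analysis will be conducted separately for patients in BOAO Pilot Zone and Hong Kong SAR CDARS".
- Section 8.3.2: "In Hong Kong SAR CDARS database, only adverse event of interest" (hepatotoxicity, interstitial lung disease/pneumonitis and renal toxicity) will be documented and analysed. The full list of safety endpoints is attached to BOAO.
- Section 8.7.3: "All patients participating in the study who meet the eligibility criteria will be included in the safety analysis", with counts and proportions for the outcomes defined in section 8.3.2.

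Section 9.3 adds that Hong Kong patient records and datasets do not go to the sponsor.

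**The concern.** The precision statement is the protocol's only justification of sample size, and it concerns the primary (safety) objective. It describes a combined cohort of 115, while the analysis section provides for two separate cohorts of about 100 and about 15. For most safety endpoints, including the one used as the example, Hong Kong contributes no data, so even a pooled analysis could not reach 115 for them.

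A reader who relies on section 8.5 or the abstract will expect the main safety proportions to be known to within about 9 percentage points. That is slightly optimistic for BOAO. It gives no idea of what the Hong Kong cohort can show on the only safety endpoints it supplies.

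**Working it through.** **Inputs**

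- Regional counts: BOAO about 100, Hong Kong about 15 (section 8.5).
- Formula: half-width of the confidence interval, "based on the normal approximation to the binomial distribution" (section 8.5), e = Z × √(p(1 − p)/n).
- Z = 1.96 for α = 0.05. The protocol gives this as an example, and it reproduces the table.
- Proportions: 50, 40, 30, 20 and 10% (Table 1).

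**Step 1: reproduce the stated figure.** At p = 0.5 and n = 115, e = 1.96 × √(0.25/115) = 1.96 × 0.04663 = 0.0914, that is ±9.14%. The other four rows also reproduce (8.95, 8.38, 7.31 and 5.48%). Table 1 contains no arithmetic error.

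**Step 2: find the n of each planned safety analysis.**

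| Endpoint | BOAO | Hong Kong |
|---|---|---|
| Three adverse events of interest | about 100 | about 15 |
| All other safety endpoints, including the grade 3 or worse example | about 100 | not collected (8.3.2) |

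Section 8.7.2.1 keeps the two columns apart, so no cell has n = 115.

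**Step 3: apply the same formula to those n.**

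- BOAO, p = 0.5: 1.96 × √(0.25/100) = 1.96 × 0.05 = 0.0980.
- Hong Kong, p = 0.5: 1.96 × √(0.25/15) = 1.96 × 0.1291 = 0.2530.

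| Proportion | Stated, n = 115 | BOAO, n = 100 | Hong Kong, n = 15 |
|---|---|---|---|
| 50% | ±9.14% | ±9.80% | ±25.3% |
| 40% | ±8.95% | ±9.60% | ±24.8% |
| 30% | ±8.38% | ±8.98% | ±23.2% |
| 20% | ±7.31% | ±7.84% | ±20.2% |
| 10% | ±5.48% | ±5.88% | ±15.2% |

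At 50%, the BOAO margin is 9.80 − 9.14 = 0.66 points wider than the stated figure. The Hong Kong margin is 25.30/9.14 = 2.8 times as wide.

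**Step 4: check with exact (Clopper-Pearson) limits.** For 50 of 100 they are 39.8% to 60.2%, a half-width of 10.2 points, close to the formula's 9.8. For 8 of 15 they are 26.6% to 78.7%, a half-width of 26.1 points. At n = 15 the formula breaks down for lower proportions: at 10% its lower limit would be 10 − 15.2 = −5.2%. No events in 15 patients has an exact upper limit of 21.8%. For Hong Kong, exact or Wilson limits are therefore the better way to state precision.

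**The case against.** The strongest reply is that little hangs on the figure, and this largely stands. The objectives are descriptive, no hypothesis is tested, and all eligible patients are taken where operationally feasible. The count is called tentative and is to be confirmed during data cleaning. For the example endpoint the correction is 0.66 points. No threshold or recruitment target rests on ±9.14%. This limits the importance of the point but does not remove the inconsistency: the count is tentative, while the mismatch between pooled precision and separate analyses is fixed in the text.

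A second reply is that the words about the largest margin only explain why 50% was chosen at a fixed 115. That is a fair reading, and in that sense the sentence is true. Nor does the protocol ever attribute ±9.14% to Hong Kong. The correct criticism is that Hong Kong has no precision statement, not that one was given and inflated.

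A third reply is that pooling is implied, because the primary analysis waits for both regions (section 8.7.1.2) and all eligible patients enter the safety analysis (section 8.7.3). The first of these sets timing and the second sets inclusion. Neither plans a combined estimate, and section 8.7.2.1 excludes one.

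A reader might infer more than the document supports:

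- **That BOAO-only events will be divided by 115, diluting the rates.** Section 8.7.2.1 separates the regions, and section 8.7.3 points back to section 8.3.2, where the regional restriction is stated. Read together, these give the BOAO denominator.
- **That results will carry poorly performing normal-approximation intervals.** The formula is used for planning only; no interval method is prescribed for the reported proportions.
- **That the absence of intervals for adverse event proportions is a gap.** That can be left to the analysis plan, to which section 8.7.2.1 defers detail.

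**Conclusion.** The point holds as a consistency error that should be corrected. Section 8.5 and the abstract state precision for 115 pooled patients, and sections 8.7.2.1 and 8.3.2 leave no analysis of that size. By the protocol's own formula the worst case is about ±9.8% for BOAO and about ±25% for Hong Kong. The latter applies only to the three adverse events of interest.

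This rests on the protocol's approximate counts of 100 and 15. The 100 assumes that all BOAO sites are eligible; fewer sites would widen the BOAO margin further. It also rests on reading section 8.7.2.1 as it stands, with no pooled summary planned elsewhere. The study's design and conduct are unaffected.

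**What to change.** In section 8.5, replace the single column of Table 1 with two: BOAO (n = 100, all safety endpoints) and Hong Kong (n = 15, adverse events of interest only). Exact or Wilson limits are preferable for Hong Kong because n is small. Change the headline there and in the abstract to worst cases of about ±9.8% and about ±25%.

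Alternatively, if a combined figure is wanted, state explicitly that the three adverse events of interest will also be summarised for both regions together. Keep N = 115 for those endpoints only, and reconcile this with the separate analyses in section 8.7.2.1 and the restriction on Hong Kong data in section 9.3. The example endpoint would still need the BOAO figure.

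As a clarification, add one sentence to section 8.7.3 saying that endpoints collected only in BOAO use the BOAO denominator.

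The cost of the regional restatement is an edit to one table and a few sentences, with no extra patients or data. The BOAO figure becomes slightly less favourable, and the Hong Kong limitation becomes visible.

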8.6 Data Management

BOAO Pilot Zone

Data relevant for the study will be extracted in the eCRF specifically designed for this study. Electronic case report forms must be completed for each patient enrolled in the study. All data recorded will be anonymized. The data extracted on the eCRFs will be captured in a clinical data management system (CDMS)/electronic data capture (eDC). The CDSM/eDC will be fully validated to ensure that it meets the scientific, regulatory, and logistical requirements for the study before it is used to capture data from this study. Before using the CDMS/eDC, all users will receive training on the system and study-specific training. Data will be extracted at the investigational center by appropriately designated and trained personnel. Data will be verified using the data source by the study monitor and reviewed for consistency by data curation using both automated logical checks and manual review. All data extracted will be approved by the investigator at the investigational center. This approval acknowledges the investigator's review and acceptance of the data as being complete and accurate.

Protocol Number: 20240175

Date: 27 March 2025 Page 28 of 47

All medical and health related terms will be coded using Medical Dictionary for Regulatory Activities (MedDRA). Medical and health related terms include AEs, medical procedures, clinical characteristics, clinical diagnosis, names and qualitative results of laboratory tests, etc. All prior and ongoing therapy and medications will be coded according to the Anatomical Therapeutic Chemical Classification System based on generic names. Other social-economic characteristics and geospatial information are complicated according to dictionaries published by the government.

The processes for database curation are consistent across data sources. Data extraction and analysis will be performed according to the applicable practices of data vendor's and Amgen's and will be performed by dedicated personnel trained to work for this study. These personnel will be responsible for data curation, accuracy, quality, completeness, and internal consistency.

Hong Kong SAR

CDARS is created for the delivery of health care. In order to use the data source for research, analytical files must be built that define the study cohort and algorithms are used to identify exposures, outcomes and covariates. Best practices according to China NMPA (China NMPA, 2021) will be used for the reporting of the detailed information behind these operational and design decisions to allow other researchers to reproduce the conduct of study.

